- l. Blood samples for WBCT will be collected on Day 3 pre-rivaroxaban dosing and post-rivaroxaban at 3.75 hrs. and post-study drug at 15, 30, and 45 minutes, 1, 2, 4, 6, 8, and 24 hours. Only subjects with at least 25% increase of clotting time from pre-rivaroxaban level on day 3 will be randomized
- m. Blood samples for PK assessment of rivaroxaban and ciraparantag and its metabolite will be collected on Day 3 pre-rivaroxaban dosing and post-rivaroxaban at 3.75 and post-study drug at 15, 30, and 45 minutes, 1, 2, 4, 6, 8, and 24 hours.
- n. Follow-up will be performed by telephone on Day 7-10. Subjects may be discharged from the study after the telephone call if all AEs have resolved to the satisfaction of the Investigator.

LIST OF ABBREVIATIONS AND DEFINITIONS OF TERMS

ABBREVIATION	DEFINITION
AE	adverse event
ALT	alanine aminotransferase
ANOVA	analysis of variance
aPTT	activated partial thromboplastin time
AST	aspartate aminotransferase
AUC	area under the concentration versus time curve
AV	Atrioventricular
BAP	1,4-Bis(3-aminopropyl)piperazine
BMI	body mass index
BP	blood pressure
bpm	beats per minute
CFR	Code of Federal Regulations
CI	confidence interval
C _{max}	maximal concentration
C ₂₄	Observed quantifiable analyte concentration in the sampled matrix at the 24-hour time point
C _{last}	Last observed quantifiable analyte concentration in the sampled matrix
CRF	case report form
CRO	contract research organization
ECG	Electrocardiogram
EDC	electronic data capture
EDTA	ethylenediaminetetraacetic acid
E _{max}	maximum effect
E _{min}	minimum effect
FIIa	factor IIa

ABBREVIATION	DEFINITION
FXa	factor Xa
F1.2	prothrombin fragments F1 and 2
FDA	Food and Drug Administration
FSH	follicle stimulating hormone
GCP	good clinical practice (refers to ICH and CFR)
HBsAg	hepatitis B surface antigen
HCV-Ab	hepatitis C virus antibody
HDPE	high density polyethylene
HIPAA	Health Insurance Portability and Accountability Act
HIV	human immunodeficiency virus
HR	heart rate
ICF	informed consent form
ICH	International Conference on Harmonization
IEC	independent ethics committee
IMPD	Investigational Medicinal Product Dossier
IND	Investigational New Drug
IRB	institutional review board
IV	Intravenous
LMWH	low molecular weight heparin
LLOQ	lower limit of quantification
LOQ	limit of quantification
NOAC	new oral anticoagulants
NS	normal saline
MedDRA	Medical Dictionary for Regulatory Activities
PD	pharmacodynamics
PK	Pharmacokinetic

ABBREVIATION	DEFINITION
PoC	point-of-care
PT	prothrombin Time
QTcF	QTc Fridericia
RR	respiratory rate
SAE	serious adverse event
SAP	statistical analysis plan
SBP	systolic blood pressure
SOC	System Organ Class
SOP	standard operating procedures
SUSAR	serious unexpected serious adverse reaction
$t_{1/2}$	half-life
t_{last}	time of C_{last} , obtained directly from the observed concentration versus time data
TEAE	treatment-emergent adverse event
TEG-R	thromboelastography reaction time
Temp	Temperature
TFPI	tissue factor pathway inhibitor
T_{max}	time of the maximum observed activity value
TMF	trial master file
UFH	unfractionated heparin
ULN	upper limit of normal
WBCT	whole blood clotting time
WHO	World Health Organization

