- Complete reversal is defined as a return of mean WBCT to $\leq 110\%$ of baseline up to and including 1 hour following test article administration.
- Complete and sustained reversal of anti-coagulation is defined as a return of mean WBCT to $\leq 115\%$ of baseline at all time points between 1 and 8 hours following test article administration. Dose escalation or de-escalation will be determined by this criterion.

Details of all statistical analyses will be specified in a separate statistical analysis plan (SAP) that will be finalized prior to data base lock.

Date of Original Protocol:

Prepared in: Microsoft Word 2013

STUDY PROCEDURES:

Day→ Procedure ↓	Screening ^a	Treatment Period					Follow-up
	Day -36 to -1	Day -1 Check-in	Day 1	Day 2	Day 3	Day 4	Day 7-10
Written informed consent	X						
Inclusion/exclusion criteria	X ^b	X					
Demographic data	X						
Height	X						
Weight	X	X					
Medical/ surgical history	X						
Medication history	X						
Physical exam ^{c, d}	X	X					X
Vital signs (BP and HR), RR and temp ^{c, e}	X	X	X	X	X	X	
Safety laboratories ^{c, f}	X	X					X
Fecal occult blood ^f		X					
Drug and alcohol screen ^g	X	X					
Viral hepatitis/HIV serology ^g	X						
12-lead ECG ^{c, h}	X	X	X	X	X	X	
Urine pregnancy test ⁱ	X						X
Serum pregnancy test ⁱ		X					
Admission to CRU ^j		X					
Randomization						X	
Rivaroxaban administration ^k			X	X	X		
Study drug administration ^k						X	
Experimental safety biomarker ^f			X		X		
PD measurements ^{c, l}			X	X	X	X	
PK sample collections ^m			X	X	X	X	
Adverse event monitoring	X	X	X	X	X	X	X
Concomitant medication	X	X	X	X	X	X	X
Discharge from clinical site							X
End of the study participation ⁿ							X

- a. Screening procedures are to be conducted -36 to -1 day before check-in on Day -1. All subjects will be provided lifestyle and dietary guidelines appropriate for an anticoagulant study and for fecal occult blood testing. If the screening visit takes place within 3 weeks prior to check-in, the check-in procedures may be modified to exclude redundant procedures at the discretion of the Investigator.
- b. Subjects should conform to the inclusion/exclusion criteria for the duration of the study. If a subject violates an inclusion or exclusion criterion at any point during the study, he/she may be removed from the study and replaced.
- c. When timing for assessments coincide, PD assessments will be performed first followed by PK assessment(s) and then safety assessments.

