1.2.2 PER977-01-002

This was a single-blind, placebo-controlled, sequential group, ascending ciraparantag dose study in healthy volunteers. Ten subjects were enrolled in each dose cohort and randomized in an 8:2 ratio to ciraparantag: placebo. All subjects in all cohorts received UFH 5000u by IV bolus injection followed immediately by 5000u administered by IV infusion over 3 hours (~1667u/hour).

Six cohorts of 10 subjects had been enrolled and had received 60 mg, 120 mg, 180 mg, 240 mg, 300 mg, and 360 mg ciraparantag, respectively. Cohort 4 (240 mg) only was performed as a two-period treatment where each subject received a single dose of ciraparantag alone during Period 1 and during Period 2, each subject received UFH followed by a single dose of ciraparantag.

Perosphere had planned to advance dosing to 480 mg ciraparantag, but the study was closed early for business reasons. Current clinical study plans involve a return to a protocol investigating the reversal of unfractionated heparin by ciraparantag following completion of studies with edoxaban and enoxaparin. There were no safety concerns that lead to the early termination. No dose limiting toxicities or TEAEs of concern were observed.

Following ciraparantag dosing, over the 60 mg to 360 mg dose levels administered in the study, there were no apparent differences in WBCT for the active treatments compared to placebo.

Complete, partial, and no reversal for WBCT were observed at the same rate for all PER977 doses combined and placebo group. There were no apparent dose-related relationships for any of the reversal categories. There were no statistically significant differences between geometric least-squares means in ciraparantag treatments compared to placebo group for percent of baseline WBCT at most time points and for PD parameters. The WBCT return to baseline was achieved at similar times, two-hour or four-hour time points, across active treatments and placebo group.

For the secondary endpoints, there were no statistically significant differences for active ciraparantag treatments versus placebo in most comparisons for PoC-aPTT and the procoagulant biomarkers TEG-R, D-dimer, F1.2, and TFPI.

Across the 60 mg to 360 mg ciraparantag dose levels, assessments of relationship between dosage and reversal of anticoagulation (complete reversal versus partial or reversal) and exposure response showed no statistically significant correlations.

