Dysgeusia	0	0	1 (12.5)	0	1 (3.1)	0
Respiratory, Thoracic, and Mediastinal Disorders						
Epistaxis	1 (12.5)	0	0	0	1 (3.1)	0
Throat Tightness	0	0	0	0	0	0
Vascular Disorders						
Flushing	1 (12.5)	3 (37.5)	5 (62.5)	0	9 (28.1)	0

[figure not shown]
A total of 30 subjects (75%) were included in the PD population. Across the three active treatments (ciraparantag 60 mg, 120 mg, and 180 mg [ciraparantag 100 mg, 200 mg, and 300 mg] in Cohorts 1-3), the mean percent-of-baseline WBCT dropped to $\leq 120\%$ by 20 minutes after the end of the ciraparantag injection and remained below 120% for the remainder of the 24-hour period. The maximum effect (E_{max}) was consistently observed at 2 minutes after the completion of the 10-minute injection. The mean percent-of-baseline WBCT maximum effect (E_{max}) were comparable across the active ciraparantag 60 mg, 120 mg and 180 mg (ciraparantag acetate 100 mg, 200 mg, and 300 mg) treatments (120.77%, 119.57%, and 127.08%, respectively) versus 144.02% in the ciraparantag 15 mg (ciraparantag acetate 25 mg) x 4 dose cohort and 140.63% in the placebo group.

Figure 2: Percent of Baseline (A-B) WBCT for All Treatments

A. Percent of Baseline Full Interval

B. Percent of Baseline Partial Interval (pre-study drug to 6 hour post final dose)

*All doses expressed as ciraparantag acetate

Complete reversal (WBCT \leq 120% at the 1-hour post study drug administration and remaining \leq 120% for the 1 to 6-hour interval) was observed in 100% of subjects in Cohorts 1, 2, and 3 (60 mg, 120 mg, and 180 mg ciraparantag [100 mg, 200 mg, 300 mg ciraparantag acetate], respectively), 71.4% in Cohort 4 (ciraparantag 4 x 15 mg [25 mg ciraparantag acetate]) and no subject in the placebo group. Partial reversal (120% to \leq 190% at the 1-hour post-study drug administration and for the 1 to 6-hour interval) was observed in 28.6% in Cohort 4 (ciraparantag 4 x 15 mg [25 mg ciraparantag acetate]) and 100% in the placebo group.

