The pharmacodynamics results show that at pre-study drug on Day 3, mean observed WBCT after edoxaban dosing increased to similar levels in the placebo group and ciraparantag treatments. Over the one to six hours postdose interval (inclusive) after the first ciraparantag dose, complete reversal for WBCT was achieved in a higher percentage of subjects in the active treatments (82.9% for all doses) compared to the placebo group (60.0%). Across the 30 mg ciraparantag to 360 mg PER977 treatments, the rate of complete reversal at 30 mg was slightly lower (62.5%) while the rate was similar for 60 mg or higher dose levels (88.9% to 100%). Both evaluable subjects (100%) in the 15 mg PER977 treatment had partial reversal. None of the subjects in any of the placebo or active treatments had percent-of-baseline WBCT >190% at any time point (i.e., no reversal).

Results of statistical comparisons showed ciraparantag had no impact on re-anticoagulation with edoxaban as measured by WBCT at pre-study drug on Day 4 versus pre-study drug on Day 3. Over the 1 to 6 hour postdose interval (inclusive) after the second ciraparantag dose on Day 4, the rates of complete reversal were comparable to Day 3. Overall, 88.6% of the subjects in the active ciraparantag treatments and 53.3% of subjects in the placebo group had complete reversal. Across the 30 mg to 360 mg active treatments, the rate of complete reversal was slightly lower (66.7%) for 180 mg while the rate was similar for all other dose levels (87.5% to 100%). None of the subjects in any of the placebo or active treatments had percent-of-baseline WBCT >190% at any time point (i.e., no reversal).

Treatment comparisons of percent-of-baseline WBCT showed lower values compared to placebo following 60 mg to 360 mg ciraparantag on Day 3 that were statistically significant at most time points between five minutes to three hours after the end of injection (geometric least-squares [LS] ratios ranged from 86.52% to 93.70%); and following 30 mg to 360 mg ciraparantag on Day 4 at most time points between five minutes to six hours after the end of injection (geometric LS ratios ranged from 84.91% to 95.71%). On both study days, WBCT at different dose levels in the active ciraparantag treatments returned to baseline within the 0.083-hour to 0.75-hour time points. Post-baseline WBCT in placebo-treated subjects did not decrease to baseline level until the 1-hour (Day 4) to 1.5-hour (Day 3) post-study drug time point.

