9.8 Analysis of the Primary PD Endpoint (WBCT)

Definition of Reversal of Anticoagulation

- Complete reversal is achieved for a treatment group if the mean WBCT is $\leq 110\%$ of baseline at any post-baseline time point up to and including 1 hour following test article administration. Complete reversal is achieved for a subject if WBCT is $\leq 110\%$ of baseline at any post-baseline time point up to and including 1 hour following test article administration.
- Complete and sustained reversal of anti-coagulation is achieved for a treatment group if the mean WBCT is $\leq 115\%$ of baseline at all time points between 1 and 8 hours (inclusive) following test article administration. Complete and sustained reversal of anti-coagulation is achieved for a subject if WBCT is $\leq 115\%$ of baseline at all time points between 1 and 8 hours (inclusive) following test article administration.

Statistically Significant Complete Reversal

- Statistically significant complete reversal, relative to mean placebo WBCT, is defined as $p < 0.05$, (one tailed) from the comparison of means between treatment and placebo at 15, 30, 45 minutes or 1 hour post study drug administration as measured by one-way Analysis of Variance at study completion. Distribution diagnostics will be performed to assure assumptions associated with using ANOVA are met. Analysis of Means (ANOM) methods will be used to compare means and variances across groups. These methods will be appropriate to test if any of the group means are statistically different from the overall mean or if the group standard deviations are statistically different from the root mean square error (RMSE). Tukey HSD multiple comparison procedure will be used to test for all pairwise differences among the means (Tukey 1953, Kramer 1956). This test is an exact alpha-level test if the sample sizes are the same, and conservative if the sample sizes are different (Hayter 1984).

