#### Statistically Significant Complete Reversal

- Statistically significant complete reversal, relative to mean placebo WBCT, is defined as  $p < 0.05$ , (one tailed) from the comparison of means between treatment and placebo at 15, 30, 45 minutes or 1 hour post study drug administration as measured by one-way Analysis of Variance (ANOVA) at study completion. Distribution diagnostics will be performed to assure assumptions associated with using ANOVA are met. One-tailed Dunnett's test will be used for comparisons of treatment means.

Analysis of Means (ANOM) methods will also be used to compare means and variances across groups. These methods will be appropriate to test if any of the group means are statistically different from the overall mean or if the group standard deviations are statistically different from the root mean square error (RMSE).

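### The 1 to 8 h sustained-reversal criterion has no placebo term and no formal placebo test is specified after 1 h, so a return to baseline without drug effect would count as sustained reversal

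*Protocol*

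**What the plan says.** Protocol 9.8 and SAP 4.7.1 share the definition: "Complete and sustained reversal of anti-coagulation is achieved for a treatment group if the mean WBCT is" at or below 115% of baseline at all time points from 1 to 8 h inclusive. A matching definition applies to each subject. Baseline is the Day 3 pre-rivaroxaban sample (Protocol 9.7, SAP 4.7.1). The scheduled WBCT times in the window are 1, 2, 4, 6 and 8 h.

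The Protocol synopsis gives the group-mean form and adds: "Dose escalation or de-escalation will be determined by this criterion". Current section 9.8 has no such sentence. Protocol 5.9 gives the dose decision to a group that reviews pharmacodynamic, adverse event, laboratory and ECG data, and it names no criterion and no placebo reference.

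The test against placebo is a one-way ANOVA with p < 0.05, one-tailed, taken "from the comparison of means between treatment and placebo at 15, 30, 45 minutes or 1 hour post study drug administration". The SAP uses a one-tailed Dunnett test for it. Analysis of Means is added, but it compares groups with the overall mean and no time points are given.

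Placebo is displayed. SAP 3.5 pools it in all tabulations, and SAP 4.7.1 asks for counts and percentages at or below 110% and 115% at each time point, and for a summary of the reversal category.

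**The concern.** The criterion asks whether clotting time is back near its starting value. It does not ask whether ciraparantag brought it there. Study drug is given 4 h after rivaroxaban, so the window covers roughly 5 to 12 h after an oral anticoagulant dose, when the anticoagulant effect may be fading by itself. The concurrent placebo group can tell the two explanations apart, but at 2, 4, 6 and 8 h it enters neither a specified test nor a rule.

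The study aims to find a dose that fully reverses rivaroxaban and also a partial or no-effect dose (Protocol 5.9). If WBCT falls to 115% or less without drug, an inert dose meets the sustained criterion. The lower boundary, planned at 30 mg, is the most exposed. A statement that reversal lasted to 8 h would then not be separated from rivaroxaban wearing off.

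**Working it through.** **1. Earlier placebo experience, as the protocol reports it**

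| Study | Placebo result |
|---|---|
| Repeat-dose edoxaban (1.2.4) | Complete reversal over 1 to 6 h: 60.0% on Day 3 (active 82.9%). Day 4: "88.6% of the subjects in the active ciraparantag treatments and 53.3% of subjects in the placebo group had complete reversal". Placebo WBCT "did not decrease to baseline level until the 1-hour (Day 4) to 1.5-hour (Day 3) post-study drug time point" |
| Unfractionated heparin (1.2.2) | "Complete, partial, and no reversal for WBCT were observed at the same rate for all PER977 doses combined and placebo group" |
| Enoxaparin (1.2.3) | Complete reversal (at or below 120%, 1 to 6 h) in 100% of the 60, 120 and 180 mg cohorts "and no subject in the placebo group" |
| Single-dose edoxaban (1.2.1) | 30 to 180 mg showed reversal versus placebo for the full 24 h |

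The first two rows show that WBCT can meet a reversal definition without drug effect. The last two point the other way.

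**2. Precision of the edoxaban placebo rates.** The counts are not printed. The percentages fit 9/15 = 60.0% and 8/15 = 53.3% (30 also fits as a denominator), and 29/35 = 82.9% and 31/35 = 88.6%. On 15 placebo subjects, the exact 95% intervals are 32% to 84% and 27% to 79%. The rates are high but imprecise.

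**3. How far WBCT must fall without drug.** The fraction of the excess to be lost by 1 h is (start − 115)/(start − 100).
- Start 125% (the entry minimum): 10/25 = 40%.
- Start 150% (assumed): 35/50 = 70%.

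Every subject enters at 125% or more, so 40% is the least that a cohort mean would have to lose.

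**4. Chance that an inert cohort passes at 1 h.** The documents give no SD for percent-of-baseline WBCT after rivaroxaban. Assume 12 points and n = 12 (3:1 of 16). The standard error is 12/√12 = 3.46, and P = Φ((115 − m)/3.46).
- m = 110: Φ(1.443) = 0.93.
- m = 115: 0.50.
- m = 120: Φ(−1.443) = 0.07.

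**5. Chance that it passes at all five times.** Simulated with assumed between-subject SD 8 and within-subject SD 9 (single-time SD √(64 + 81) = 12.0), with the excess at 1 h halving every 2 h, every 4 h, or staying flat.

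| True mean at 1 h | Every 2 h | Every 4 h | Flat |
|---|---|---|---|
| 110% | 0.91 | 0.91 | 0.76 |
| 115% | 0.48 | 0.43 | 0.14 |
| 120% | 0.07 | 0.05 | <0.01 |

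The result turns almost entirely on where WBCT sits without drug, which only the placebo group can show.

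**6. What a placebo comparison could resolve.** Averaging five times gives a subject-level SD of √(64 + 81/5) = 8.96. The one-sided 95% margin, unadjusted, is:
- 12 v 16 pooled placebo: 8.96 × √(1/12 + 1/16) × t(0.95, 26) = 8.96 × 0.382 × 1.706 = 5.8 points.
- 12 v 4 after Cohort 1: 8.96 × √(1/12 + 1/4) × t(0.95, 14) = 8.96 × 0.577 × 1.761 = 9.1 points.

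Dunnett adjustment widens both.

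**7. Why compare means.** With one-sided Fisher tests of 12 v 16 and a placebo rate of 60.0%, power is 26% for an active rate of 82.9% and 40% for 88.6%. Comparing responder rates would be weak exactly where the problem arises.

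**The case against.** The case against has force on several points.

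- A reader might infer that the window has no placebo comparison at all. That is not so. Its first point, 1 h, is in the Dunnett test, and the SAP tabulates counts at or below 115% at each time point with pooled placebo shown. A reader of the tables would see placebo meeting the threshold if it did. What is missing is a formal comparison after 1 h and a rule that uses what is displayed.
- A dose that behaves like placebo should also fail the early test against placebo, apart from type I error. This protects the label of statistically significant complete reversal. The sustained label is defined separately and does not require that test to be passed.
- A reader might infer that dose selection will be misled. The sentence tying dosing to the criterion stands only in the synopsis. Section 5.9 leaves the decision to a group reviewing pharmacodynamic data, and the blinding described covers only subjects and coagulation testers. The dose schema is not shown and may contain a rule. An effect on dosing is possible but not demonstrated.
- A reader might carry 60.0% and 53.3% over to this trial. They are subject-level rates over 1 to 6 h, after edoxaban, with study drug given at 3 h and a threshold not stated for that study. They show that spontaneous return can happen and do not estimate its rate here.
- Return to own baseline is a legitimate pharmacodynamic target. Requiring every dose to beat placebo could deny the label to an effective dose once rivaroxaban has worn off in both groups. This objection stands, and the fix respects it.

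**Conclusion.** The point holds in limited form. The sustained criterion has no placebo term, no formal placebo test is specified after 1 h, and no rule uses the placebo data that will be tabulated. Whether this would produce a false label depends on how WBCT behaves on placebo 5 to 12 h after rivaroxaban, which the documents do not establish: the repeat-dose edoxaban and heparin studies suggest that return without drug effect is possible, while the enoxaparin and single-dose edoxaban studies do not. If the true mean without drug effect at 1 h is 110%, an inert cohort would probably meet the criterion (about 76 to 91%); at 120% it would rarely do so (7% or less). These probabilities rest on assumed SDs and time courses. The change is worth making because it uses data already collected and decides whether sustained reversal can be attributed to ciraparantag.

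**What to change.** **Protocol 9.8 and SAP 4.7.1.** Keep the 115% definition as a description of return to baseline. Add a prespecified one-tailed Dunnett comparison of each dose with pooled placebo on mean percent-of-baseline WBCT over 1 to 8 h, from a repeated-measures model with estimates at 1, 2, 4, 6 and 8 h. Apply the 115% criterion to the pooled placebo group as well. If placebo also meets it, attribute sustained reversal to ciraparantag only when the dose group is lower than placebo; otherwise report that the dose group was at or near baseline and not distinguishable from placebo.

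**Synopsis and Protocol 5.9.** State that the review group sees the placebo time course pooled to date, and that if placebo also meets the 115% criterion, that criterion alone does not set the next dose. Between cohorts this is descriptive, because only 4 placebo subjects are available after Cohort 1.

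**Cost.** One added model and a few sentences. No extra subjects, samples or visits: the 16 planned placebo subjects already follow the same WBCT schedule. The limit is precision. Differences smaller than the margins in step 6 will not be resolved, and separation at late times will be hard as rivaroxaban wears off.
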